- To explore the relationship between maternal hemodynamic parameters and fetal cardiac function and morphology in our population

METHODS

Study design This is a prospective monocentric interventional study with the use of the medical device UltraSonic Cardiac Output Monitor (USCOM®).

Study Population: Singleton pregnancy with a diagnosis of CHD performed at the Fetal Medicine Unit of Fondazione Policlinico A. Gemelli IRCCS during the study period and delivered at Fondazione Policlinico A. Gemelli IRCCS.

Study duration

The study has an expected duration of 36 months (three years). The study will begin when the ethics committee has issued a favorable opinion.

Inclusion criteria

The inclusion criteria are:

- Informed consent accepted
- Maternal Age >18 years
- Singleton pregnancy with a viable fetus at >20 weeks of gestation, with a diagnosis of CHD detected on antenatal ultrasound assessment and postnatally confirmed.

Exclusion criteria

The exclusion criteria are:

- Multiple pregnancy
- Pregnancy complicated by aneuploidy, genetic syndrome, or major structural fetal abnormality.
- Maternal congenital heart disease (GUCH)
- Maternal known cardiac disease

Variables and procedures

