Maternal hemodynamics assessment: Hemodynamic indices will be obtained using the USCOM® system. Women will undergo a hemodynamic investigation at the time of first diagnosis of CHD

during pregnancy or at the first assessment in Fondazione Policlinico A. Gemelli during pregnancy and then every two weeks until delivery. An additional hemodynamics evaluation will be performed in the post-partum period (in the 72 hours immediately after delivery). All hemodynamic assessment will be performed under standardized conditions. Maternal height, weight and brachial blood pressure will be obtained prior to hemodynamic assessment. USCOM® system utilizes continuous-wave Doppler, with a non-imaging probe in the suprasternal notch, to obtain velocity-time integrals of transaortic blood flow at the left ventricular outflow tract. Using an internal anthropometric algorithm, which correlates the outflow tract diameter with the patient's height, USCOM-1A multiplies the velocity-time integral by the aortic root diameter to calculate stroke volume. By measuring the time interval between each Doppler profile, heart rate (HR) can be calculated. CO (stroke volume \times HR) and SVR (MAP/CO) are calculated after inclusion of maternal mean arterial pressure. Participants remain in a semi recumbent position and a small amount of conducting gel is applied to their skin at the level of the suprasternal notch. The Doppler probe is applied and moved through three dimensions to ensure that the velocity of blood was being measured at the left ventricular outflow tract and not in the more distal aorta. Each Doppler acquisition used for analysis must register a minimum of two consecutive Doppler profiles (cardiac cycles). All hemodynamic measurements were performed by trained operators. USCOM-1A has been in clinical use since 2015. Its repeatability and reproducibility have been assessed in adult, pediatric and pregnant populations, demonstrating excellent agreement between operators with sufficient training (15; 16).

ENDPOINTS

Primary endpoint: To identify the maternal hemodynamic parametrics changes in pregnancies complicated by congenital heart diseases and immediately after delivery.

Secondary endpoints:

- prevalence of cases of preeclampsia in our population of pregnancies complicated by congenital heart disease
- To investigate association between maternal hemodynamic profile and perinatal outcome

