- To calculate correlation coefficients between the maternal hemodynamic parameters to the specific heart defect type
- To calculate correlation coefficients between the maternal hemodynamic parameters and fetal cardiac function and morphology parameters

STATISTICAL ANALYSIS PLAN

Sample size calculation

108 patients will be recruited

Statistical analysis

The sample will be described in its clinical and demographic characteristics by descriptive statistics techniques. In depth, qualitative data will be expressed as absolute and relative percentage frequency, whilst quantitative variables either by mean and standard deviation (SD) or median and interquartile range (IQR), as appropriate.

To verify the Gaussian distribution of quantitative variables, the Shapiro-Wilk test will be applied.

The discrete variables will be compared by Chi Square or Fisher Exact test.

Correlation analysis between hemodynamic parameters and variables related to the type of congenital heart defect of the fetus will be carried out by calculating and testing Pearson's and/or Spearman's correlation coefficient, when necessary Kendall's correlation coefficient will be used. Likewise, correlation analysis between hemodynamic parameters and fetal cardiac function parameters will be carried out.

To identify any differences in mean between baseline and immediate postpartum, continuous variables will be compared with the T test for paired data and/or the Wilcoxon test when appropriate.

Regression analysis will be performed to explore the relationship between maternal hemodynamic parameters and maternal and perinatal outcome and fetal cardiac parameters.

Mixed-effects models for longitudinal data will be fit to identify potential changes over time in maternal hemodynamic parameters also in relation to fetal cardiac parameters, controlling for any confounding variables.

All results will be considered statistically significant when $p < 0.05$.

All analyses will be conducted with R statistical software (R, cran, 2023).

Safety/Adverse Event Management

All adverse events observed during the study will be collected and recorded.

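### The paired baseline-to-postpartum test mixes antenatal change over an interval set by referral timing with the change at delivery, so it cannot alone address the postpartum part of the primary endpoint

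*Protocol*

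**What the plan says.** Four parts of the Protocol bear on this point.

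- **Primary endpoint (ENDPOINTS):** "To identify the maternal hemodynamic parametrics changes in pregnancies complicated by congenital heart diseases and immediately after delivery". One sentence covers both change during pregnancy and change after delivery.
- **Measurement schedule (Maternal hemodynamics assessment):** "Women will undergo a hemodynamic investigation at the time of first diagnosis of CHD". Alternatively, this reading is taken when the woman first attends the centre, and readings are then repeated at two-week intervals up to delivery. There is then one postpartum reading, "in the 72 hours immediately after delivery".
- **Entry (Inclusion criteria):** "Singleton pregnancy with a viable fetus at >20 weeks of gestation, with a diagnosis of CHD detected on antenatal ultrasound assessment". No upper gestational limit is set.
- **Analysis (Statistical analysis):** "To identify any differences in mean between baseline and immediate postpartum, continuous variables will be compared with the T test for paired data", with the Wilcoxon test as alternative. Separately, "Mixed-effects models for longitudinal data will be fit to identify potential changes over time in maternal hemodynamic parameters", with control for confounders that are not named.

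The word baseline appears in the paired comparison but is not tied to any visit. The mixed-model sentence does not give the time scale, and does not say whether the postpartum reading enters the model. The paired test is the only analysis that names the postpartum reading.

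**The concern.** If baseline is the first assessment, it comes at a different point in pregnancy for each woman. One woman may be measured soon after 20 weeks and another a few weeks before delivery. Both contribute a postpartum-minus-baseline difference with equal weight, although one difference spans several months of pregnancy and the other a few weeks.

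The mean of these differences therefore reflects three things at once: how the parameter moves during pregnancy, how early women were diagnosed or referred, and what happens around delivery. Only the last answers the postpartum part of the primary endpoint. A sizeable mean difference could arise with no change at delivery, and a real change at delivery could be cancelled by an opposite antenatal trend. Two centres with identical physiology but different referral patterns would report different means.

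The schedule already provides readings every two weeks up to delivery, so a value close to delivery will usually exist. The paired comparison, read naturally, does not use it.

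**Working it through.** **Plan's own figure.** There is none to reproduce for this comparison. The Protocol gives 108 patients and a 0.05 threshold, but no effect size, SD, power or drift.

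**Step 1: decomposition.** For one woman,

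postpartum − first visit = (end of pregnancy − first visit) + (postpartum − end of pregnancy).

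The first bracket is antenatal change over her own interval, and the second is the change at delivery. The paired test estimates the mean of the sum. It equals the mean change at delivery only if the mean antenatal change is zero.

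**Step 2: inputs.**

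- From the Protocol: n = 108, threshold 0.05, entry after 20 weeks, readings every two weeks until delivery.
- Assumed, because the Protocol does not give them: a two-sided test; first visit uniform over 20 to 36 weeks; delivery at 38 weeks; linear drift of 0.01, 0.02 or 0.03 per week, in units of the SD of the paired difference; and the same SD whichever antenatal reading is used.

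**Step 3: mean gap and mean contribution of drift.**

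- Mean first visit = (20 + 36)/2 = 28 weeks, so the mean gap = 38 − 28 = 10 weeks.
- Contribution = drift × gap: 0.01 × 10 = 0.10 SD; 0.02 × 10 = 0.20 SD; 0.03 × 10 = 0.30 SD.
- With the last two-weekly reading, the gap is 0 to 2 weeks, mean 1 week, so the contribution is 0.01, 0.02 or 0.03 SD.

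**Step 4: dependence on referral.** At 0.02 SD per week, a woman first seen at 20 weeks contributes 0.02 × 18 = 0.36 SD of drift. One first seen at 36 weeks contributes 0.02 × 2 = 0.04 SD.

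**Step 5: scale against what the study can detect.** Detectable paired difference = (z₀.₉₇₅ + z_power)/√n.

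- 80% power: (1.960 + 0.842)/√108 = 0.27 SD.
- 90% power: (1.960 + 1.282)/√108 = 0.31 SD.

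Drift of 0.03 SD per week thus yields a mean difference (0.30 SD) of about the size that the sample can detect.

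**Step 6: simulation** (108 pairs, 4,000 runs per setting, paired t test).

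True change at delivery zero:

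| Drift per week | First visit: mean difference | First visit: p < 0.05 | Last antenatal reading: mean difference | Last antenatal reading: p < 0.05 |
|---|---|---|---|---|
| 0.01 SD | 0.10 SD | 17% | 0.01 SD | 5% |
| 0.02 SD | 0.20 SD | 54% | 0.02 SD | 6% |
| 0.03 SD | 0.30 SD | 87% | 0.03 SD | 6% |

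True change at delivery 0.3 SD, drift in the opposite direction:

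| Drift per week | First visit: p < 0.05 | Last antenatal reading: p < 0.05 |
|---|---|---|
| 0 | 87% | 87% |
| −0.01 SD | 55% | 85% |
| −0.02 SD | 19% | 83% |
| −0.03 SD | 5% | 80% |

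In the last row the drift contributes −0.03 × 10 = −0.30 SD and cancels the change at delivery exactly.

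**The case against.** The strongest reply is that the test does what its sentence says. It looks for a difference in mean between two time points, and a paired t or Wilcoxon test is valid for that. The sentence does not claim to isolate an effect of delivery. This stands. A reader might infer that the rejection rates of 17% to 87% are false-positive rates. They are not: with drift present, the first-visit and postpartum means really differ and rejection is correct for the literal hypothesis. The rates show only how poorly the result would serve as evidence of change at delivery.

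Second, baseline as first visit is an inference, and an SAP not shown may define it. This also stands, although no other visit in the schedule fits the word as naturally.

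Third, the planned mixed-effects models could separate antenatal trend from the step at delivery. Nothing excludes the postpartum reading from them, and no analysis is named as primary. So it would go too far to infer that the paired test is the sole analysis of the primary endpoint or that the endpoint cannot be answered. What remains is that the Protocol does not assign the delivery contrast to the model.

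Three further inferences are unsupported. The drift cannot be called normal pregnancy drift, because there is no control group to separate normal from disease-related change. Loss of women without a postpartum reading is common to any paired test, and the study population is limited to women who deliver at the centre. The 72-hour window is a bounded design choice, not an error.

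Finally, the last antenatal reading has its own bias. If delivery is prompted by rising blood pressure, that reading may catch a peak and exaggerate a later fall. This is a good reason not to make it the main contrast.

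**Conclusion.** The point holds within limits. On the natural reading of baseline, the paired difference combines antenatal change over a woman-specific interval with the change at delivery, and its mean varies with referral timing. It is a valid description of overall first-visit-to-postpartum change. It cannot alone support a statement about change immediately after delivery.

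The structural argument needs no figures, but the size does, and the documents supply none. Under the assumed timing, drift of 0.01 to 0.03 SD per week gives 0.1 to 0.3 SD with no change at delivery. If mean antenatal drift is zero, the distortion is zero.

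This is a should-fix matter. The stated aim is largely descriptive, the necessary readings are already scheduled, and a suitable model is already planned.

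**What to change.** 1. Define baseline explicitly as a named visit.
2. State that the change immediately after delivery is estimated from the planned mixed-effects model, with gestational age at each reading as the time axis and a term for the postpartum reading. Setting that reading's gestational age to the value at delivery makes the term the difference between the postpartum level and the modelled level at delivery.
3. Keep the first-visit-to-postpartum paired comparison as description. Report with it the gestational age at first visit and the interval to the postpartum reading.
4. Optionally, add a paired test against the last scheduled antenatal reading (about 0 to 2 weeks before delivery) as a supporting analysis, with a note that this reading may catch a peak when rising blood pressure prompts delivery.

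The cost is a change of wording, a date for each reading, and a slightly more complex model whose delivery contrast depends on an adequate shape for the antenatal trend. No new measurements are needed.
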